## SYNOPSIS

**Sponsor:** Theracos Sub, LLC

**Name of Finished Product:** Bexagliflozin Tablets, 20 mg

**Name of Active Ingredient:** Bexagliflozin

**Study Title:** An Integrated Assessment of the Safety and Effectiveness of Bexagliflozin Tablets, 20 mg, for the Management of Essential Hypertension

**Protocol Number:** THR-1442-C-603

**Study Phase:** 2/3

### Overall Design:

This integrated assessment consists of two studies, 603A and 603B, to be carried out sequentially in a common study population. Participating subjects will be informed of the trial design and their consent to participate in both studies will be obtained in a single consent form.

### Primary Objective of Study 603A

In study 603A, the effectiveness of bexagliflozin tablets, 20 mg, will be assessed in a study population randomized 1:1 to receive either active agent or placebo. The primary endpoint will be the change from baseline (Day 1) to week 12 of the average ambulatory systolic blood pressure (SBP) of the bexagliflozin group compared to the placebo group.

### Secondary Objectives of Study 603A

Additional effectiveness outcomes will be assessed from ambulatory as well as seated office blood pressure measurements.

Secondary endpoints based on mean ambulatory SBP will include the proportion of subjects who achieve a reduction of mean ambulatory SBP of 10 mm Hg or greater and the proportion of subjects who achieve a mean ambulatory SBP of 135 mm Hg or less at week 12.

Secondary endpoints based on seated office SBP will include the placebo-adjusted change from baseline to week 12 in seated office SBP and the proportion of subjects who achieve a mean seated office SBP of 140 mm Hg or less at week 12.

Secondary endpoints based on mean ambulatory DBP will include: the placebo-adjusted change in mean ambulatory DBP from baseline to week 12; the proportion of subjects who achieve a mean ambulatory DBP of 87 mm Hg or less at week 12; and the proportion of subjects who achieve a reduction of mean ambulatory DBP of 4 mm Hg or greater at week 12.

Secondary endpoints based on seated office DBP will include the placebo-adjusted change from baseline to week 12 in seated office DBP and the proportion of subjects who achieve a mean seated office DBP of 90 mm Hg or less at week 12.

An additional objective of study 603A will be an assessment of the maximum and minimum treatment effect (peak-trough ratio) by ABPM SBP at week 12.

### **Primary Objective of Study 603B**

In study 603B, the effectiveness of bexagliflozin tablets, 20 mg, will be assessed by measurement of the loss of the treatment effect following randomized withdrawal. All study entrants will first be dosed with bexagliflozin tablets, 20 mg, for 12 weeks. At week 12 the participants will undergo a 1:1 randomization to bexagliflozin tablets, 20 mg, or placebo. The primary endpoint will be the change from week 12 to week 24 of the mean ambulatory SBP of the bexagliflozin group compared to the placebo group.

### **Secondary Objectives of Study 603B**

The secondary objectives of study 603B are based on separate assessments of effects on mean ambulatory and seated office systolic and diastolic blood pressures.

Study 603B will also include a population pharmacokinetic assessment between weeks 6 and 12, when all participants will be receiving bexagliflozin tablets, 20 mg.

### **Integrative Objectives of Study 603A and 603B**

Integration of measures collected in studies 603A and 603B will be used to assess consistent effects on mean ambulatory SBP/DBP after 12 weeks of bexagliflozin treatment, as well as longer treatment periods, i.e., 24 weeks or 36 weeks of bexagliflozin treatment.

In addition, the seated office systolic and diastolic blood pressure will be collected at more frequent intervals than for ambulatory monitoring, and the changes over time will be evaluated to provide a composite profile of treatment effect as a function of time.

### **Integrated Safety Objectives:**

The integrated safety objectives will assess the hazard ratio for adverse events associated with bexagliflozin exposure compared to placebo in all segments of both studies in which a placebo-exposed cohort is present. The assessments will include:

- the frequency and severity of all adverse events
- the frequency and severity of adverse events of special interest
- changes in concomitant medication use
- changes in laboratory test values
- changes in cardiac rhythm determined by 12-lead ECG
- changes in vital signs
- effects on general health detected by physical examination

### **Design:**

THR-1442-C-603 is an integrated assessment of the potential utility of bexagliflozin tablets, 20 mg for the treatment of essential hypertension. It is composed of two studies, 603A and 603B, measuring effects in a common population.

### **Study 603A**

Approximately 680 male or female adult subjects who exhibit an office seated blood pressure  $\geq 140$  mm Hg and  $< 180$  mm Hg, and who are taking no more than 4 anti-hypertension medications will be enrolled in study 603A. In the desired population,  $> 10\%$  of the subjects will have a baseline ABPM  $> 160$  mm Hg and  $< 30\%$  of the subjects will have type 2 diabetes

mellitus.

Subjects who meet the eligibility criteria at the screening visit (visit 1) will start a 2 week run-in period. At the end of the run-in period, subjects who have not been disqualified by laboratory testing results based on samples drawn at the screening visit, who have been compliant in taking the run-in medication, and who exhibit a seated SBP  $\geq$  140 mm Hg and  $<$  180 mm Hg will be eligible for participation. At the investigative site the subjects will take the last dose of run-in drug, will be fitted with an ABPM device and will start a 24-h ambulatory blood pressure monitoring (ABPM) to establish the baseline ABPM SBP and DBP. On the following day, qualified subjects who have completed the 24-h ABPM with a mean 24-h SBP  $\geq$  135 mm Hg will be randomly assigned to receive bexagliflozin tablets, 20 mg or placebo, using an interactive web response system (IWRS). If  $<$  64 SBP readings are recorded, the ABPM must be repeated within 2 days. Prior to randomization, subjects who cannot successfully complete the ABPM within two attempts will be considered screen failures.

Randomization will be stratified according to diabetes status (history of T2DM or not), renal function (eGFR  $\geq$  60 or not), presently medicated for hypertension or not, and ABPM SBP ( $<$  160 mm Hg or not).

A bottle of double blind study drug will be dispensed to each randomized subject with an instruction to take one tablet daily in the morning with a glass of water before or after breakfast. It will be recommended that subjects take the study drug at about the same time every day except on the days of scheduled site visit when the study drug will be administered at the investigational site.

A six week visit to the investigational site will allow seated office measures of systolic and diastolic blood pressure to be recorded.

At week 12 (end of study), the subject will visit the investigational site, consume the final tablet, and be fitted for ABPM.

An interim non-binding futility analysis will be conducted when approximate 50% of the randomized subjects have completed study 603A. The data will be analyzed by an independent group that is not part of the study management team. Results from the analysis will be reviewed by an independent Data Monitoring Committee (DMC).

### **Study 603B**

Upon returning to the investigational site to surrender the ambulatory monitor at the conclusion of study 603A, subjects will begin participation in study 603B. They will receive a 12-week supply of bexagliflozin tablets, 20 mg.

At week 6 (cumulative week 18) subjects will return to the investigational site for measurement of seated systolic and diastolic blood pressures.

At week 12 (cumulative week 24) subjects will visit the investigational site to consume the bexagliflozin tablet and to be fitted with an ambulatory monitor to record their baseline mean blood pressure.

The following day, subjects will be randomized 1:1 to receive a 12-week supply of

bexagliflozin tablets, 20 mg or bexagliflozin tablets, placebo. Assignment to the active or placebo arm will be balanced to approximately equalize the representation in each arm of the following groups:

- Subjects not requiring rescue medication prior to week 24 and exhibiting a  $> 20$  mm Hg reduction in mean SBP between Day 1 and cumulative 24
- Subjects not requiring rescue medication prior to week 24 and exhibiting a  $> 5$  mm Hg and  $\leq 20$  mm Hg reduction in mean SBP between Day 1 and cumulative 24
- Subjects not requiring rescue medication prior to week 24 and exhibiting a  $\leq 5$  mm Hg reduction in mean SBP between Day 1 and cumulative 24
- Subjects requiring rescue medication prior to week 24

An assessment of bexagliflozin population pharmacokinetics (PK) will also be conducted, to include approximately 200 subjects. Samples will be taken between weeks 6 and 12. The population PK study design and analysis plan will be described in a separate designated study protocol and the analysis will be reported separately.

Integrated management of hypertension, including use of rescue medications

Subjects will be counseled to be compliant with all their medications, to exercise regularly, lose weight if overweight or obese, adopt a diet rich in fruits, vegetables and low-fat dairy products (the DASH diet, with appropriate modifications for participants with CKD), reduce sodium intake and alcohol consumption to recommended levels. Patients who smoke will be encouraged to stop. Every effort will be made to secure the continued participation of the subjects.

Rescue medications are recommended following the guidance below if the SBP shows an increase of 30 mm Hg from baseline or exceeds 189 mm Hg in office measurements over 3 consecutive days.

### **Guidance for Hypertensive Rescue Medication Use**

Study 603A, cumulative weeks 1-6

- Follow procedures for visits 10 and 11 as early termination visits to obtain 24-h ABPM and collect safety data
- Rescue medication should not be administered unless hypertensive emergency appears imminent. In those situations, refer the subject to seek urgent care in a clinic or hospital. Subject should withdraw from participation in the study and see primary care provider to start or intensify anti-hypertensive therapies

Study 603A, cumulative weeks 7-12

- Follow procedures for visits 5 and 6 to obtain 24-h ABPM and collect safety data
- Start visit 6 (start of 603B) without rescue medication. If a hypertensive emergency appears imminent, refer the subject to seek urgent care in a clinic or hospital. Prescribe rescue medication at Visit 7 if SBP shows an increase of 30 mm Hg from baseline or exceeds 189 mm Hg in office measurements and continue study activities

#### Study 603B, cumulative weeks 13-18

- Obtain 24-h ABPM and collect safety data
- Rescue medication should not be administered unless hypertensive emergency appears imminent. In those situations, refer the subject to seek urgent care in a clinic or hospital. Prescribe rescue medication at Visit 7 if SBP shows an increase of 30 mm Hg from baseline or exceeds 189 mm Hg in office measurements and continue study activities

#### Study 603B-Cumulative weeks 19-24

- Obtain 24-h ABPM and collect safety data
- Prescribe rescue medication if SBP shows an increase of 30 mm Hg from baseline or exceeds 189 mm Hg in office measurements and continue study activities

#### Study 603B-Cumulative weeks 25-36

- Obtain 24-h ABPM and collect safety data
- Prescribe rescue medication if SBP shows an increase of 30 mm Hg from baseline or exceeds 189 mm Hg in office measurements and continue study activities

Additional study procedures for safety and efficacy endpoint assessment will be performed as outlined in the study schedule.

The effectiveness and safety analyses will be conducted after all subjects have completed or withdrawn from study 603B.

To allow safety data to be collected for up to 36 weeks of exposure, the study will not be stopped for overwhelming efficacy. The DMC will review the unblinded safety data at approximately 2 month intervals and may recommend protocol modifications or early termination due to safety concerns.

#### **Study Population:**

A total of 680 patients with essential hypertension will be initially randomized. The subjects must be:

1. Male or female with age  $\geq 20$  years
2. Diagnosed with essential hypertension and exhibiting an office seated SBP  $\geq 140$  and  $< 180$  mm Hg  
Unmedicated or currently treated by a stable regimen for hypertension. Unmedicated subjects are subjects who have never taken pharmacotherapy for hypertension or have not taken any anti-hypertensive medication for at least 12 weeks. To be considered stable, a regimen must exhibit no change in dose or frequency for the 4 weeks prior to the screening visit
3. If female and of childbearing potential, willing to use an adequate method of contraception and to not become pregnant for the duration of the study. Adequate contraceptive measures include, but are not limited to, oral contraceptives, intrauterine devices, Depo-Provera, Norplant, hormonal contraceptive implants, bilateral tubal

ligation, partner with vasectomy, condom or diaphragm plus contraceptive sponge, foam, or jelly, and abstinence

4. Willing and able to return for all clinic visits and to complete all study-required procedures
5. Able to self-medicate during the run-in period, omitting no more than one day of dosing (confirm at visit 2)
6. Shown to have a seated SBP  $\geq 140$  and  $< 180$  mm Hg (confirm at visit 2)
7. Shown to have a mean 24 h SBP  $\geq 135$  mm Hg (at visit 3)

**Test Product, Dose, and Mode of Administration:**

Bexagliflozin tablets, 20 mg or placebo, to be taken by mouth once daily in the morning

**Duration of Treatment:** up to 36 weeks

**Study 603A**

**Primary effectiveness assessment**

- Change from baseline (Day 1) to week 12 of the 24-hour mean SBP

**Secondary effectiveness assessments include:**

- the proportion of subjects who achieve a reduction of mean ambulatory SBP of 10 mm Hg or greater;
- the proportion of subjects who achieve a mean ambulatory SBP of 135 mm Hg or less;
- the placebo-adjusted change from baseline to week 12 in seated office SBP;
- the proportion of subjects who achieve a seated office SBP of 140 mm Hg or less at week 12;
- the placebo-adjusted change in mean ambulatory DBP from baseline to week 12;
- the proportion of subjects who achieve a mean ambulatory DBP of 87 mm Hg or less at week 12;
- the proportion of subjects who achieve a reduction of mean ambulatory DBP of 4 mm Hg or greater;
- the placebo-adjusted change from baseline to week 12 in seated office DBP;
- the proportion of subjects who achieve a mean seated office DBP of 90 mm Hg or less at week 12.

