## 9.6 Secondary Efficacy Endpoints

Secondary efficacy endpoints will be accessed without multiplicity adjustment. Analyses will be primarily based on ITT analysis sets.

Absolute values and changes from baseline (Day 1 for study 603A or Week 12 value for study 603B) in vital signs measurements, pulse pressure, body weight, peak-trough ratio of ABPM SBP, and HbA1c will be summarized descriptively. Mean treatment effects will be estimated based on ANCOVA using similar method as described for the primary endpoint.

The responder assessments, such as the proportion of subjects who achieve specific goals, will be summarized by frequency table; logistic regression will be used to analyze the treatment effect with 95% CIs for the fraction responding within each treatment group and between treatment groups. Analyses will be based on all observed assessments prior to rescue medication or study end. In addition, a sensitivity analysis by assuming non-responder for subjects who had no post baseline assessments prior to early withdrawal of the study or initiation of the rescue medication, will also be performed.

In addition, changes in mean ambulatory SBP/DBP or office seated SBP/DBP after 12, 24, or 36 weeks of bexagliflozin treatment will also be summarized using combined 603A and 603B evaluations.

Detailed analyses will be defined in the statistical analysis plan.

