8.1. STUDY 603A

For all analyses at Week 12, LOCF will be used for subjects who lack Week 12 assessments or who require intensification of anti-hypertensive therapy. Only post-baseline values before rescue medication will be carried forward.

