8.1.2. Secondary Efficacy Endpoints and Analyses

The secondary efficacy endpoints include mean ambulatory and seated office SBP, mean ambulatory and seated office DBP. Secondary efficacy endpoints will be accessed without multiplicity adjustment. Analyses will be primarily based on ITT analysis set.

8.1.2.1. The proportion of subjects who achieve a reduction of mean ambulatory SBP of 10 mm Hg or greater

Subjects who achieve a reduction of mean ambulatory SBP of ≥ 10 mm Hg will be summarized using frequency and percentage by treatment arm. Logistic regression will be used to analyze the treatment effect. The model will include diabetes status (history of T2DM or not), renal function (eGFR at screening as continuous variable), pre-treatment status (presently medicated for hypertension or not), baseline mean

ambulatory SBP value and randomized treatment. The LS Mean responding proportion and 95% CI will be estimated within each treatment group from a logistic regression model. A p-value for comparison by treatment group will also be provided. Two different outcomes will be explored:

- Responder will be defined using the last-post baseline value. If a subject received rescue medication, the value prior to the initiation of rescue medication will be used (primary analysis);
- Subjects with no post baseline assessments prior to early withdrawal from the study or initiation of the rescue medication will be considered as non-responders (sensitivity analysis).

8.1.2.2. The proportion of subjects who achieve ambulatory SBP of 135 mm Hg or less

The summary and analyses will be provided as in section 8.1.2.1.

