8.1.2.3. The placebo-adjusted change from baseline to week 12 in seated office SBP

A summary and ANCOVA model will be presented as in section 8.1.1.1. The model will use baseline seated office SBP in place of baseline mean ambulatory SBP.

8.1.2.4. The proportion of subjects who achieve a mean seated office SBP of 140 mm Hg or less at week 12

A summary and analysis will be presented as in section 8.1.2.1. The model will use baseline seated office SBP in place of baseline mean ambulatory SBP.

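### In 603A, a subject who withdraws or is rescued with an at-goal last reading is a week-12 responder in both planned responder analyses, so the sensitivity analysis cannot test dependence on drop-out or rescue

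*Protocol*

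**What the plan says.** The Synopsis lists six responder endpoints for 603A. Four are ambulatory: SBP fall of at least 10, SBP at most 135, DBP at most 87, and DBP fall of at least 4 mm Hg. Two are office measures: SBP at most 140 and DBP at most 90. Three of the six bullets name week 12, for example "the proportion of subjects who achieve a seated office SBP of 140 mm Hg or less at week 12". SAP 8.1 treats all of them as week-12 analyses: "For all analyses at Week 12, LOCF will be used for subjects who lack Week 12 assessments or who require intensification of anti-hypertensive therapy". It adds that only readings taken before rescue are carried forward.

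SAP 8.1.2.1 gives two versions of the responder analysis:

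- Main: "Responder will be defined using the last-post baseline value". For rescued subjects, "If a subject received rescue medication, the value prior to the initiation of rescue medication will be used".
- Sensitivity: "Subjects with no post baseline assessments prior to early withdrawal from the study or initiation of the rescue medication will be considered as non-responders".

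The later responder sections refer back to these rules. SAP 8.1.2.4, for office SBP, says "A summary and analysis will be presented as in section 8.1.2.1. The model will use baseline seated office SBP in place of baseline mean ambulatory", which changes only the baseline covariate.

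Protocol 9.6 has the same structure. For the main analysis it says "Analyses will be based on all observed assessments prior to rescue medication or study end". It then adds "a sensitivity analysis by assuming non-responder for subjects who had no post baseline assessments prior to early withdrawal of the study", or before rescue began.

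**The concern.** The two versions differ only for subjects who have no usable post-baseline reading. If a subject has any such reading and the last one is at goal, both versions score a success, even if the subject then left the study or needed more blood-pressure treatment before week 12.

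A responder sensitivity analysis normally exists to show whether the comparison survives when early withdrawal and rescue are treated as failure. Here agreement between the two tables would say nothing about that. The primary endpoint is better protected. SAP 8.1.1.2 has one analysis without subjects who lack the scheduled week-12 assessment, and a tipping-point analysis that sets withdrawn and rescued subjects to missing. The responder endpoints have no counterpart.

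**Working it through.** **1. Reading the rules together.** Take a 603A subject with no scheduled week-12 value, or with rescue before it.

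| Last post-baseline reading before withdrawal or rescue | Main analysis | Sensitivity analysis |
|---|---|---|
| At goal | Responder | Responder |
| Above goal | Non-responder | Non-responder |
| None | No value | Non-responder |

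Only the third row changes.

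**2. Which endpoints have such readings.**

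- Office SBP and DBP: visit 4 (week 6) records office pressure. Withdrawing subjects are to complete exit procedures with vital signs (Protocol 6.14 and 7). SAP 6.4 uses an early-termination or unscheduled visit when the scheduled one is missing. A reading will usually exist, except for losses before week 6 without an exit visit.
- Ambulatory endpoints: the Schedule of Events has no ABPM between baseline and visit 5. An earlier value can come only from an early-termination ABPM or from visits 5/6 held early. A drop-out with neither becomes a non-responder in the existing sensitivity analysis, which then works as intended.
- Rescue: the trigger in Protocol 5.7 is systolic only, and entry sets no lower limit for DBP, so a subject can meet the trigger while at a DBP goal. For office SBP, a rise of 30 from an entry value of at least 140 gives about 140 + 30 = 170 or more, which is not at goal. For SBP goals, what remains is mainly rescue below the trigger. The definition of rescue in Protocol 5.7 and the investigator's discretion in 5.2.2 allow this.

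**3. The plan's own figure.** Protocol 9.2 expects 8% drop-out by week 12: 680 x 0.92 = 625.6, which reproduces its 626. The plan gives no rate for any responder endpoint and no rescue rate.

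**4. Size from drop-out.** Per arm, 680 / 2 = 340 and 340 x 0.08 = 27.2 drop-outs. Let q be the share of drop-outs whose last reading is at goal (assumed, 0.30 to 0.60).

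- q = 0.30: 27.2 x 0.30 = 8.2 subjects; 8% x 0.30 = 2.4 points.
- q = 0.60: 27.2 x 0.60 = 16.3 subjects; 8% x 0.60 = 4.8 points.
- Outer limits: 0 points at q = 0 and 8 points at q = 1.

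**5. Effect on the between-arm difference.** The planned difference minus the difference with drop-outs as failures is d_B x q_B - d_P x q_P, where d is drop-out in each arm.

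- Drop-out 10% v 6% (assumed), equal q: 0.04 x 0.30 = 1.2 points to 0.04 x 0.60 = 2.4 points. The sign depends on which arm loses more.
- Drop-out 8% in both arms, equal q: 0. Both rates are inflated alike.
- Drop-out 8% in both arms, q of 50% v 30%: 0.08 x 0.20 = 1.6 points.

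For scale, with an assumed response rate of 42% the standard error of the difference is 100 x sqrt(2 x 0.42 x 0.58 / 340) = 3.8 points. The 1.2-2.4 points are about 0.3-0.6 of that.

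**The case against.** The strongest case against is that the reach is narrow and the effect small. Four of the six endpoints are ambulatory and are touched only through an early or exit recording. An exit reading supersedes the week-6 one, so a subject at goal at week 6 but above goal on leaving is a non-responder in both analyses. These are secondary endpoints without multiplicity adjustment, and the primary endpoint has its own checks. All of this stands. It limits the point but does not remove it: no planned responder analysis counts withdrawal or rescue as failure once a post-baseline value exists.

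Some stronger readings are tempting, and the documents do not support them:

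- A reader might infer that any earlier at-goal reading is enough. It must be the last one before withdrawal or rescue.
- A reader might infer that subjects rescued for very high SBP are scored as office-SBP successes. The rescue guidance calls for exit visits or visits 5/6 when the trigger is met, and by the arithmetic above the office SBP should then exceed 140.
- A reader might infer a bias of known size and direction on the DBP goals, because rescue may be commoner on placebo. No rescue rates are given. Assumed rates of 1-3% on drug and 3-8% on placebo, with 50-80% of these subjects at goal, span (3% - 3%) = 0 to (8% - 1%) x 0.8 = 5.6 points, which is too wide to serve as an estimate.
- A reader might infer that the analysis favours the drug. The sign depends on drop-out and last readings in each arm, and neither is known.

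It could also be said that scoring a subject as a DBP failure because SBP met a trigger would turn a DBP goal into a composite. That is right, and the fix does not use the trigger.

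**Conclusion.** The point holds, within limits. The responder sensitivity analysis in SAP 8.1.2.1 and Protocol 9.6 leaves unchanged every withdrawn or rescued subject whose last reading is at goal, so it cannot show whether the result depends on them. The main exposure is in the two office endpoints. For the ambulatory endpoints the exposure is limited to early recordings. Rescue matters mainly for the DBP goals and for rescue below the trigger.

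The plan's 8% drop-out and an assumed 30-60% at goal give 2.4-4.8 points per arm of responders without a week-12 value. Whether they would have been at goal at week 12 is unknown. The shift of 1.2-2.4 points in the difference rests on an assumed 10% v 6% drop-out and equal shares at goal. At equal drop-out and equal shares only the rates are inflated. The rescue part cannot be sized. The primary endpoint is not affected. The change should be made, but nothing here invalidates the trial.

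**What to change.** Keep LOCF as the main responder analysis. In SAP 8.1.2.1, and so by reference in 8.1.2.2, 8.1.2.4, 8.1.2.6, 8.1.2.7 and 8.1.2.9, redefine the sensitivity analysis. Count as a non-responder every randomized subject who has no valid value in the scheduled week-12 window (visits 5/6, within 3 days either way) or who started rescue medication before that value. State that early-termination values and values from visits 5/6 held early do not count as week 12 in this analysis. This must be explicit, because SAP 6.4 uses nominal visits without analysis windows. Align Protocol 9.6, or list the change in SAP Section 12.

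The cost is a short SAP addition, matching protocol wording, and one changed responder flag in six logistic models already planned. It uses visit dates and rescue start dates that are already collected, and leaves trial conduct unchanged. Responder rates in the sensitivity table will be slightly lower.
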